## 4.0 STUDY DESIGN

### 4.1 Description of Study

This is a pilot study of a 2-arm randomized trial with a 2:1 initial allocation to exercise intervention or waitlist control (see Appendix B for study schema). The intervention group will then be randomly assigned (1:1) to receive either a 12-week aerobic exercise (AE) intervention or a 12-week resistance exercise (RE) intervention.

At 12 weeks, the intervention group will be assessed for intervention response, defined as a  $\geq 5\%$  increase in 6-minute walk distance (6MWD) over baseline. Non-responders to either AE or RE will receive 12 weeks of combined AE+RE. Intervention responders will continue the exercise intervention in their current assignment, either AE or RE alone, for the additional 12 weeks.

This study will employ a waitlist control. After 24 weeks, the waitlist control group will receive a digital copy of sessions provided to the intervention arm. The control and intervention arms' schedule of evaluations will be identical across all 24 weeks of the trial.

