#### 4.3 Study Procedures

#### 4.3.1 Recruitment

This project will recruit 30 study participants through a multi-pronged approach:

Seattle Cancer Care Alliance (SCCA) clinics: At SCCA, we will work with the breast oncology clinic research team to obtain a list of potentially eligible research participants that will include patient name, phone number, and mailing address. This eligibility will be based on age and approximate end date of chemotherapy or Herceptin therapy. Potentially eligible participants identified through SCCA will receive a mailed letter endorsed by their oncologist inviting them to call the study coordinator for more information and/or screening. The study team may follow up proactively with a phone call no less than two weeks after sending the letter.

Breast cancer support groups in the community: Study information will be provided to breast cancer support groups in the community by sharing study flyers (paper, electronic, or Web versions) with the organizers of these groups and by giving presentations at in-person group events, as permitted by organizers.

Re-contacting previous breast cancer research participants: The pool of previous breast cancer research participants will be generated from past projects under the purview of the study's principal investigators or shared from affiliate investigators. Previous participants or candidates will be contacted via phone, email, or mailed letter, depending on what information is available to the study PIs.

The UW ITHS Leaf tool: The University of Washington's Leaf system will be used to generate an identifiable cohort of potentially eligible patients in the UW Medicine system. The study will query the database for patients who meet key eligibility criteria and who have recently visited the UW Medicine system for treatment. Candidates generated from this list will be sent a letter that describes the study and invites them to contact the study team should they be interested in participation. The study team may follow up proactively with a phone call no less than two weeks after sending the letter.

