In addition, we will explore potential moderators of the intervention, namely baseline BMI and physical activity, and adherence to the intervention for Objectives 2 and 3, and as guidance in designing the subsequent large-scale intervention. First, we will stratify upon BMI to explore whether the intervention showed greater benefit in those with higher BMI. Then we will repeat this for baseline physical activity to explore whether the intervention showed greater benefit in those with lower baseline physical activity. Next, the level of adherence to the intervention will be evaluated by examining the accelerometry data output in conjunction with the self-reported physical activity data. We will also conduct qualitative analyses utilizing data from the elicitation interviews conducted at the end of the intervention. This analysis will summarize data collected from the participants' into themes.

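### Moderation by BMI and baseline activity is to be read from strata, with no estimate of the between-stratum difference; separately, adherence is listed as a moderator for Objective 2 although controls have none

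*Combined protocol and SAP*

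**What the plan says.** Section 10.0 states that "we will explore potential moderators of the intervention, namely baseline BMI and physical activity, and adherence to the intervention for Objectives 2 and 3". For BMI the method is "we will stratify upon BMI to explore whether the intervention showed greater benefit in those with higher BMI". For activity it is "Then we will repeat this for baseline physical activity to explore whether the intervention showed greater benefit in those with lower baseline physical activity". For adherence the only description is that "the level of adherence to the intervention will be evaluated by examining the accelerometry data output in conjunction with the self-reported physical activity data". The section says these explorations are to help in designing the later, larger study.

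Section 10.0 gives no cut-point for BMI or activity, no arm-by-moderator term, no contrast or confidence interval for the difference between strata, and no significance level. Its generalized linear models are specified for comparisons between groups.

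On size, Section 4.3.1 says "This project will recruit 30 study participants through a multi-pronged approach", and Section 4.1 sets a "2:1 initial allocation to exercise intervention or waitlist control". Section 4.3.4 (Randomization) stratifies on AC chemotherapy history only. Section 6.2 gives the waitlist arm the same assessments but no exercise sessions during the 24 weeks.

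**The concern.** Whether benefit is greater at higher BMI or lower activity is a question about a difference between two effects. Two stratum results side by side do not estimate that difference or show its uncertainty. In a trial of 30 each stratum effect is very imprecise, so sizeable gaps arise by chance. Grouping a continuous moderator also loses information. Because the results are offered as design guidance, the exploratory label does not fully protect a reader from taking a chance gap as a lead.

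Adherence is a different fault. It arises after randomisation and exists only for people assigned sessions. In Objective 2 the comparator has no sessions, so an arm-by-adherence effect cannot be estimated. Comparing adherers with all controls would give up the randomised comparison.

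**Working it through.** The plan gives no power, precision or subgroup figure for this point, so there is none to reproduce.

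**Inputs from the documents.** N = 30 (Section 4.3.1) at 2:1 (Section 4.1) gives 20 vs 10. The feasibility benchmark of under 40% loss (Section 10.0) gives a lower bound of 30 × 0.6 = 18, or 12 vs 6.

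**Assumptions.** Median split with arms divided evenly, two-sided 0.05, and SD = 1, so effects are in SD units. None of these is in the documents.

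**Step 1: precision at 20 vs 10.**
- Overall effect: SE = √(1/20 + 1/10) = 0.387.
- One stratum, 10 vs 5: SE = √(1/10 + 1/5) = 0.548.
- Difference between strata: SE = √2 × 0.548 = 0.775.

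**Step 2: chance gaps with no true moderation.**
- P(gap > 0.5 SD) = 2 × [1 − Φ(0.5/0.775)] = 52%.
- P(gap > 0.8 SD) = 2 × [1 − Φ(0.8/0.775)] = 30%.
- At 12 vs 6 the SE of the difference is √2 × √(1/6 + 1/3) = 1.00, and the two probabilities are 62% and 42%.
- For AE vs RE as randomised (10 vs 10), the SE is √2 × √(1/5 + 1/5) = 0.894, and a gap above 0.5 SD has probability 58%.

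These figures need no reading rule based on p-values.

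**Step 3: if each stratum were tested separately at p<0.05.** Simulation with t-tests, 40,000 trials per row, and the same true effect in both strata (10 vs 5 each):

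| Common true effect (SD) | Exactly one stratum significant |
|---|---|
| 0.2 | 12% |
| 0.3 | 15% |
| 0.5 | 23% |
| 0.8 | 40% |
| 1.0 | 48% |

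Significance is counted in either direction. At 12 vs 6 in total, the rates for 0.5, 0.8 and 1.0 SD are about 16–17%, 28% and 35–36%. An interaction test on the same data rejects in about 5% of trials at any common effect.

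**Step 4: continuous versus median-split interaction.** Simulated power, with the treatment effect changing by the stated amount per SD of moderator:

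| Moderation (SD per SD) | Continuous, 20 vs 10 | Median split, 20 vs 10 |
|---|---|---|
| 0.3 | 10% | 8% |
| 0.5 | 21% | 15% |
| 0.8 | 44% | 28% |

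At 12 vs 6 and 0.8 SD per SD, power is about 25% vs 16%. Simulation error is about one percentage point. The continuous form is better throughout, but neither is powerful. With a median split, 80% power needs a between-stratum difference of (1.96 + 0.84) × 0.775 = 2.2 SD.

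**Step 5: number of looks.** Section 10.0 names 11 outcomes for Objective 2: CRF, submaximal capacity, thigh IMF:SM, four abdominal fat depots, body weight, quality of life, well-being and fatigue. If both baseline moderators were applied to all of them, that is 22 looks. Even interaction tests at 0.05 would then give 22 × 0.05 = 1.1 false positives on average. The chance of at least one is 1 − 0.95^22 = 68% if independent; the outcomes are correlated, so this is only a guide.

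**Step 6: adherence.** Section 6.2 gives controls no sessions, so adherence to the intervention has no value in the Objective 2 comparator. Controls do have accelerometry (Section 4.3.5), but that measures activity, not adherence to assigned sessions. In Objective 3 all groups exercise, so adherence is defined there, though still after randomisation.

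**The case against.** The strongest reply is that the plan contains no decision rule. It does not say that strata will be tested separately, that one significant stratum will count as moderation, or that the cut will be at the median. It does not exclude an interaction term. A reader might infer that moderation will be declared from within-stratum p-values; the documents do not say so. That part of the reply stands, and the percentages in step 3 illustrate one possible reading. They also fall to 12–15% at effects of 0.2–0.3 SD. Step 2 does not depend on such a rule, although it does assume the median split.

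A reader might also infer that chance differences will be mistaken for moderation and will send the next trial to the wrong target group. The documents do not support either claim. The primary endpoint is intervention discontinuation (Section 4.2.1), Section 10.0 makes feasibility and safety a primary consideration for launching a larger study, and nothing says the next trial's population will be chosen from these strata.

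On adherence, the only analysis described is descriptive, so calling it a moderator may be loose wording. The objection also does not reach Objective 3 in the same way, and it is not a cause of chance differences between strata. Both qualifications are accepted.

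Finally, the suggested model gains little when moderation is modest (10% vs 8% power at 0.3 SD per SD). This is correct. The case for it rests on estimating the right quantity and showing its uncertainty, more than on power.

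**Conclusion.** The point holds in limited form. The plan names a method, stratification, that does not by itself estimate the quantity asked about, and a better one costs almost nothing. Under a median split and SD = 1, a gap above 0.5 SD between strata is about as likely as not without any moderation (52%, rising to 62% at 12 vs 6). Under an assumed separate-test reading, discordant strata occur in about 12% to 48% of trials for common effects of 0.2 to 1.0 SD, against about 5% false positives for an interaction test. The documents do not show that the team will read the strata that way, or that the next trial will be misdirected.

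The adherence fault is separate and decisive for Objective 2 only. A reader might infer that adherence has no place in either objective, but it can be described in Objective 3 because everyone there is assigned exercise. It would not be a randomised comparison.

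**What to change.** In Section 10.0, replace the stratified comparisons. For BMI and for baseline activity, fit one model to all participants with outcome data: outcome on arm, baseline outcome, the continuous moderator, and arm × moderator. Report the interaction estimate with its 95% CI, labelled hypothesis-generating and not used as a decision rule. Stratum summaries may be kept as description.

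Remove adherence from the moderators for Objective 2 and describe it as a dose-response association among exercising participants. For Objective 3 it may be described, labelled as a post-randomisation, non-causal comparison.

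The cost is a change of wording, with no new data. The downsides are a linearity assumption for each moderator and an imprecise estimate: power is about 10% to 44% at 20 vs 10 for moderation of 0.3 to 0.8 SD per SD, and lower after loss to follow-up. The interval will make that imprecision visible.

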## Appendix A – Data & Safety Monitoring

### BRIEF STUDY OVERVIEW

This is a pilot study of a 2-arm SMART-design exercise intervention among breast cancer survivors with reduced cardiorespiratory fitness.

### OVERSIGHT RESPONSIBILITIES

Oversight of the trial is provided by [name], the Principal Investigator (PI), and co-investigators, [name] and [name] (“co-investigators” throughout).

### MONITORING PROCEDURES

[name] assures that informed consent is obtained prior to performing any research procedures, that all subjects meet eligibility criteria, and that the study is conducted according to the IRB-approved research plan.

Study data are accessible at all times for the PI to review. The PI and co-investigators review study conduct (accrual, drop-outs, protocol deviations) on a monthly basis. The PI reviews adverse events (AE) individually in real-time and with co-investigators in aggregate on a monthly basis. The PI and co-investigators review serious adverse events (SAEs) in real-time. The PI ensures all protocol deviations, AEs, and SAEs are reported to the IRB according to the applicable regulatory requirements.

### COLLECTION AND REPORTING OF SAEs AND AEs

For this study, the following standard AE definitions are used:

**Adverse event:** Any unfavorable and unintended sign (including an abnormal laboratory finding), symptom or disease temporally associated with the use of a medical treatment or intervention procedure, regardless of whether it is considered related to the medical treatment or intervention procedure.

**Serious Adverse Event:** Any AE that results in any of the following outcomes:

- Death
- Life-threatening
- Event requiring inpatient hospitalization or prolongation of existing hospitalization
- Persistent or significant disability/incapacity

AEs are graded according to the following scale:

**Mild:** An experience that is transient & requires no special treatment or intervention. The experience does not generally interfere with usual daily activities. This includes transient laboratory test alterations. A mild AE typically corresponds to a 1 on the NCI Common Terminology Criteria for Adverse Events (CTCAE).

**Moderate:** An experience that is alleviated with simple therapeutic treatments. The experience impacts usual daily activities. Includes laboratory test alterations indicating injury, but without long-term risk. A moderate AE corresponds to a 2 on the CTCAE.

**Severe:** An experience that requires therapeutic intervention. The experience interrupts usual daily activities. If hospitalization (or prolongation of hospitalization) is required for treatment it becomes an SAE. A severe AE corresponds to a 3 on the CTCAE.

The study uses the following AE attribution scale:

**Not related:** The AE is clearly not related to the study procedures (i.e., another cause of the event is most plausible and/or a clinically plausible temporal sequence is inconsistent with the onset of the event).

**Possibly related:** An event that follows a reasonable temporal sequence from the initiation of study procedures, but that could readily have been produced by a number of other factors.

**Related:** The AE is clearly related to the study procedures.

AEs are identified by participant self-report at each study follow up assessments (12-, 24-, 36- and 48-weeks). Participants will be asked about medical or mental health events that have happened since the previous assessment visit. AEs may also be identified during supervised (in-person or remote) exercise sessions, with an event either occurring or being reported during such sessions.

SAEs and specific procedure-associated AEs are reported to the PI and co-investigators within 24 hours. In addition, all AEs are reported according to the University of Washington AE reporting guidelines.

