## 6.0 INTERVENTION PLAN

### 6.1 Treatment Intervention Arm

Participants in the intervention group will be randomized to receive either AE or RE training. The intervention will comprise of a combination of supervised and unsupervised sessions. Supervised sessions will be led remotely via videoconferencing by a trained fitness instructor, while unsupervised sessions will involve following along with recorded videos. Training protocols will be adapted from the American College of Sports Medicine's (ACSM) guidelines and designed to progress in intensity, depending on patient tolerance.

All intervention sessions will include 5 minutes of warm up and 5 minutes of cool down. Warm up and cool down will consist of light aerobics and stretching for both groups. Sessions will occur 3 times a week, with 1 supervised and 2 unsupervised. In the first 3 weeks of resistance training, sessions will occur 2 times per week (1 supervised), to account for increased muscle soreness when starting a resistance training regimen.

Exercise intensity will be measured using the Rating of Perceived Exertion (RPE) scale, which collects respondent's perception of exertion level on a scale from 6-20. Moderate exercise will be considered a 12-13 on this scale, while 14-16 will constitute vigorous exercise.

Participants will rate their perceived exertion after each exercise session, and RPE feedback will be utilized to adjust intensity levels for participants' upcoming sessions.

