### **6.2 Waitlist Control Arm**

The waitlist control group will spend 24 weeks waitlisted for the intervention, during which time they will follow the same schedule of evaluations as the intervention group but will not receive exercise sessions. After completing 24-week assessments, the control group will receive a digital copy of sessions recorded during the intervention group and an outline of sessions for 24 weeks.

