## 10.0 STATISTICAL CONSIDERATIONS

For objective 1, we will measure the feasibility of our intervention by calculating recruitment rates (% participants enrolled of those approached), enrollment rate (% enrolled of those eligible), lost to follow-up (% who dropped out of those enrolled), intervention discontinuation rate (% of intervention participants who permanently stop the intervention for any reason by Week 24), intervention attendance (% exercise sessions attended), relative dose intensity (% completed sessions), and compliance (based on accelerometry data, self-report of exercise via questionnaires). A benchmark to determine feasibility includes <40% loss to follow-up.

In objective 2, we will start with an analysis of the safety endpoints by calculating the number and percent of adverse events that occurred during the intervention and during the waitlist control period. This analysis will be stratified by the severity of the adverse events, the seriousness of the adverse events, and by the attribution of the adverse events.

The results from above analyses (for Study Aim 1) will be a primary consideration to inform the feasibility and safety of launching a larger scale intervention from the pilot intervention. If both these sets of data provide indications that the study is feasible and safe, then the exploration of additional intervention outcomes will take place. These data will be presented in a manuscript to describe the potential for this intervention. The following analyses will explore additional intervention outcomes to inform the intervention's potential to have an impact on CRF, functional capacity, physiologic changes, and PRO in a larger scale intervention.

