## MANAGEMENT OF RISKS TO SUBJECTS

### Expected AEs

Expected AEs associated with the exercise intervention include:

- Fatigue
- Muscle Soreness
- Mild Shortness of Breath
- Mild Tachycardia
- Transient increase in blood pressure
- Lightheadedness
- Excessive Sweating
- Muscle strain or sprain

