## **DATA ANALYSIS PLANS**

[figure not shown]
As this is a pilot study, there will be insufficient numbers to conduct a well-powered interim analysis. The study team will examine SAEs and expected AEs in aggregate at the midpoint of the study to examine whether disproportionate SAEs or AEs have occurred in the intervention participants. While there is unlikely to be statistical power in interim analysis, we will conduct bi-variate statistical analysis consisting of chi-square tests to evaluate the proportion of SAEs and AEs in intervention participants versus control participants. The investigators will review this statistical analysis. Discussions of whether sufficient evidence exists for stopping the trial early will involve consideration of whether the AEs are related or unrelated to the study activities.

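### Exercisers have a roughly weekly route for detecting adverse events that controls lack, and the between-arm comparisons are not split by how events were found, so mild and moderate events lean towards apparent excess harm by an unknown amount

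*Combined protocol and SAP*

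**What the plan says.** Appendix A (Collection and Reporting of SAEs and AEs) gives two routes. The first, common to both arms, is self-report at follow-up assessments, covering the time since the last one. The second is the supervised session: "AEs may also be identified during supervised (in-person or remote) exercise sessions, with an event either occurring or being reported during such sessions".

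Section 6.1 sets the frequency for exercisers: "Sessions will occur 3 times a week, with 1 supervised and 2 unsupervised". The reduced schedule in the first three weeks of resistance training still has one supervised session a week. For controls, section 6.2 says that "they will follow the same schedule of evaluations as the intervention group but will not receive exercise sessions".

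Two between-arm comparisons of adverse events are planned:

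- Section 10.0, objective 2, descriptive: "calculating the number and percent of adverse events that occurred during the intervention and during the waitlist control period", stratified by severity, seriousness and attribution.
- Appendix A (Data Analysis Plans), at the midpoint: "The study team will examine SAEs and expected AEs in aggregate at the midpoint of the study", using "chi-square tests to evaluate the proportion of SAEs and AEs in intervention participants versus control participants".

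Section 10.0 makes the exploration of further outcomes conditional: "If both these sets of data provide indications that the study is feasible and safe".

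**The concern.** An event that an exerciser mentions at a session is recorded. The same event in a control is recorded only if she recalls it at the next visit, up to 12 weeks later. Appendix A defines mild events as transient, so they are plausibly the easiest to forget. Sessions can pick up any event that is reported there, not only exercise injuries.

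No other provision closes the gap. Section 2.4 promises open-ended questions but gives no timing. The regular communication in section 4.3.3 is for participants' concerns and retention. Section 4.3.5 marks safety as ongoing in both arms but sets no inquiry between visits. The reviews in section 8.0 and Appendix A examine events already recorded.

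Between-arm safety is a study aim (section 3.0) and a secondary endpoint (section 4.2.2). At stake is the pilot's estimate of adverse-event burden in exercisers versus controls, which is meant to inform a larger trial. As planned, it would mix a real exercise effect with extra detection.

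**Working it through.** **The plan's own figure.** There is none. The documents give no adverse-event rate, capture rate or test threshold.

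**Inputs from the documents.** 30 participants (section 4.3.1) at 2:1 (section 4.1), so about 20 exercisers and 10 controls; one supervised session a week for 24 weeks; common assessments at weeks 12 and 24.

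**Planned detection occasions.** Exercisers: 24 + 2 = 26. Controls: 2. This shows the imbalance in opportunity, not the size of the bias.

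**Assumptions (none from the documents).**

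- v = share of events caught at visits, equal in both arms: 0.75, 0.5 or 0.3.
- s = share of the missed events caught at sessions: 0.25 or 0.5.
- m = true events per person over 24 weeks, equal in both arms: 0.5, 1 or 2.
- Two-sided 5% level, uncorrected Pearson chi-square on participants with at least one event.

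**Event counts.** Exerciser capture is e = v + s(1 − v), and inflation is e/v − 1. For v = 0.3, s = 0.5: e = 0.3 + 0.5 × 0.7 = 0.65, and 0.65/0.3 − 1 = 117%.

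**Midpoint test.** Midpoint is not defined, so two readings are shown: half the sample (10 vs 5) and all 30 (20 vs 10), each with half the follow-up. P(at least one recorded event) = 1 − exp(−(m/2) × capture). For v = 0.3, s = 0.5, m = 2 this is 1 − exp(−0.65) = 0.478 in exercisers and 1 − exp(−0.30) = 0.259 in controls. All possible outcomes were enumerated, adding the probability of those with p < 0.05 and the higher proportion in exercisers.

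| v | s | e | Event inflation | False excess harm, 10 vs 5 (m = 0.5/1/2) | False excess harm, 20 vs 10 (m = 0.5/1/2) |
|---|---|---|---|---|---|
| 0.75 | 0.25 | 0.81 | 8% | 0.2/1.3/3.5% | 1.0/2.5/3.7% |
| 0.75 | 0.50 | 0.88 | 17% | 0.2/1.7/4.5% | 1.3/3.3/5.1% |
| 0.50 | 0.25 | 0.63 | 25% | 0.1/0.8/3.5% | 0.5/2.8/5.4% |
| 0.50 | 0.50 | 0.75 | 50% | 0.2/1.7/6.3% | 1.2/5.3/10.3% |
| 0.30 | 0.25 | 0.48 | 58% | 0.0/0.4/3.3% | 0.2/2.6/7.7% |
| 0.30 | 0.50 | 0.65 | 117% | 0.1/1.6/9.0% | 1.0/8.0/19.7% |

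With equal capture (s = 0) the same test gives at most 2.6% at 10 vs 5 and 2.7% at 20 vs 10. The direction is the same in every row because an added route can only add recorded events. The size depends wholly on v, s and m.

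**The case against.** The strongest reply is that the plan already stratifies. Section 10.0 breaks adverse events down by severity, seriousness and attribution, and Appendix A has a three-level attribution scale. Background events found only through weekly contact should fall largely under not related, while events seen during a session will tend to be called related. A reader might infer that real and detection-driven excess cannot be told apart at all; the documents do not support that. The separation is partial, though. Possibly related events stay ambiguous, and nothing in the documents blinds attribution to arm.

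A reader might also infer large false-alarm rates from a chi-square on 20 vs 10 participants at full follow-up. The plan contains no such test: the final comparison is descriptive, and the midpoint chi-square is the only between-arm test of adverse events. That test has no stated threshold, its power is disclaimed, and relatedness is weighed in any discussion of stopping. The error is also in the cautious direction, and feasibility is the primary endpoint. All of this stands and limits the consequence.

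Nor would a recorded excess be pure artefact. The midpoint look covers expected events, which Appendix A introduces with "Expected AEs associated with the exercise intervention include", so some real excess is likely.

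**Conclusion.** The point holds as a minor one. The detection routes differ by arm, neither between-arm comparison accounts for this, and recorded mild and moderate events will lean towards excess harm in exercisers. This assumes equal visit recall and equal follow-up; differential dropout could offset or add to it. That serious events are little affected is an inference from their being easier to recall.

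The size is unknown. On the assumed ranges the lean is modest if visits catch most events and substantial if they catch few. It does not by itself threaten the stopping discussion. The main harm is to the reading of the pilot's adverse-event burden. The point concerns exercisers versus controls; the objective 3 comparison of exercise types is not affected in the same way, because each regimen has about one supervised session a week.

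**What to change.** In section 10.0 and Appendix A:

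- Add a detection-source field to the adverse-event form (scheduled assessment, supervised session, other).
- Keep the all-source comparison, and keep every event in the listings and the real-time review.
- Beside it, including at the midpoint, report participants with at least one event elicited by the same questioning at the common week 12 and 24 assessments, over those randomised per arm, with exact confidence intervals. Ask exercisers at those visits to include events already reported at sessions; otherwise they may not repeat them and the comparison would falsely reassure.
- List session-detected events separately.
- Label the common-visit comparison a sensitivity analysis, and state that a null result does not show safety.

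The cost is one form field and some wording. The source should be recorded prospectively, since it may not be recoverable later. The downside is that the visit-only comparison omits some real harm seen at sessions and has low power. For a true doubling from 0.5 or 1 event per control, at 20 vs 10 with full follow-up and Fisher's exact test, power is 3.3-11.7% at v = 0.3, 10.1-15.9% at v = 0.5 and 12.7-24.1% at v = 0.75 (v assumed as above). It should therefore sit beside the all-source comparison and not replace it.

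Separately, Appendix A lists 36- and 48-week assessments that do not appear in sections 4.3.4 (Data Collection) and 4.3.5, which end at week 24. These passages must be reconciled.
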